#### **8.7.4 Vital signs**

Vital signs will include SBP (mmHg), DBP (mmHg), RR (breaths/min), HR (beats/min), and body temperature (°C). Observed values, change from baseline and percent change from baseline for vital signs will be summarized using an 8-number summary by visit and treatment group. In addition, the number and percentage of subjects with significant changes (per the criteria below) in vital signs from baseline will be summarized by treatment.

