### **8.3. Clinical Evaluations**

#### **8.3.1. Vital Sign Measurements, Body Temperature and Electrocardiograms**

Vital signs will include heart rate (HR), respiratory rate, and blood pressure (BP). Vital signs will be measured at times shown in the [Schedule of Assessments](#) after the subject has been supine for 5 minutes and before dosing.

Body temperature should be taken at the Screening, Day 1, and EOS visits according to site standard practices.

Resting 12-lead ECGs will be performed locally and recorded at the times indicated in the [Schedule of Assessments](#) after the subject has been supine for 5 minutes and before dosing. A standard bedside 12-lead ECG machine that calculates HR and measures the PR, QRS, QT, RR, and QTc (QTcF) intervals should be utilized. If the site does not have an ECG machine that calculates these values, the site will need to calculate the values. If a blood draw and ECG are scheduled at the same time, then the ECG should be obtained first.

The normal ranges for the ECG are as follows:

- PR: 120 - 220 msec
- QRS: 70 – 120 msec
- QT:  $\leq$  500 msec
- QTcF:  $\leq$  450 msec
- Heart Rate: 50 – 100 bpm

The PI or designee should review the ECGs in real-time for gross abnormalities and interval measurements of concern (absolute readings and for postdose ECGs, change from baseline). Ranges outside of the normal ranges listed above should be recorded as abnormal. The clinical interpretation by the PI or designee of the ECGs should be recorded on a hard copy of the ECGs (i.e., normal, abnormal clinically significant [CS] or abnormal nonclinically significant [NCS]).

The PI or designee must repeat any ECG where the QTcF interval  $>450$  msec, or absolute QT  $>500$  msec, or with a change from Baseline in QTcF  $>60$  msec. These abnormal ECGs must be repeated once regardless of whether or not the values are considered clinically significant by the PI or designee. Also, ECGs may be repeated at the discretion of the PI to account for erroneous readings.

Prior to dosing, the Baseline ECG must be reviewed to confirm that no clinically significant cardiac abnormalities are present.

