#### **11.7.5. Vital Signs**

The incidence rate of subjects with treatment-emergent vital sign changes at any postbaseline visit will be summarized. Specific criteria for the classification of treatment-emergent will be documented in the SAP. Vital sign observed, change, and percent change will be summarized by treatment over visits.

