#### **Criteria for clinically significant changes in vital signs parameters.**

##### Pulse Rate

- < 50 bpm
- >120 bpm
- 30 bpm increase from baseline

- 30 bpm decrease from baseline

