#### Blood Pressure

- SBP > 150 mmHg or DBP > 100 mmHg
- SBP > 200 mmHg or DBP > 110 mmHg

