#### Respiration Rate

- < 8 breaths/min
- 40 breaths/min

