#### Temperature

- 38.3°C
- 1.1°C increase from baseline (Baseline > 36.8°C)

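### Seven of the 12 vital-sign criteria in SAP 8.7.4, including both blood-pressure rows, are bare limits with no baseline condition, so subjects already beyond a limit before dosing count as changed

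*SAP*

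**What the plan says.** Protocol 11.7.5 sets the task: "The incidence rate of subjects with treatment-emergent vital sign changes at any postbaseline visit will be summarized". It then leaves the classification rules for treatment-emergent to the SAP.

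SAP 8.7.4 is where those rules belong. After by-visit summaries of observed values, change and percent change, it adds that "the number and percentage of subjects with significant changes (per the criteria below) in vital signs from baseline will be summarized by treatment". The words treatment-emergent do not appear there, and no rule says what the baseline value must be. The 12 criteria fall into two groups:

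- **Absolute limits (7):** both blood-pressure rows, "SBP > 150 mmHg or DBP > 100 mmHg" and "SBP > 200 mmHg or DBP > 110 mmHg"; both respiration rows, one of which is "< 8 breaths/min" and the other 40 breaths/min; pulse below 50 and above 120 bpm; temperature 38.3°C.
- **Tied to baseline (5):** pulse up or down by 30 bpm, for example "30 bpm increase from baseline"; a 1.1°C temperature rise, which also carries its own condition on the baseline value; weight up or down by 5%.

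Two rows (40 breaths/min and 38.3°C) appear without a direction sign. That may be lost in the PDF text and is not counted here as an error.

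On timing, Protocol 8.3.1 states: "Body temperature should be taken at the Screening, Day 1, and EOS visits". SAP Section 9, which lists what is dropped after the study was terminated, does not list 8.7.4.

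**The concern.** The label and most of the criteria do not match. The label promises change from baseline and the protocol promises incidence, but a bare limit measures whether a reading is beyond the limit at any time after baseline. Take a subject with systolic pressure 155 on Day 1 and 151 at Week 2. The pressure has fallen by 4 mmHg, yet the first blood-pressure row is met. Blood pressure has no baseline-relative row at all, so nothing else in its categorical summary separates new from existing elevation.

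Subjects who start beyond a limit add events to every arm for reasons unrelated to treatment. That raises all the percentages and pulls the ratio between arms toward 1. Blood pressure is not a stratification factor, so a chance imbalance at baseline would also show up in this table as an apparent drug effect, in either direction.

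Temperature has a related timing problem. Its only scheduled reading after Day 1 is at the end-of-study visit, four weeks after the last dose, so the temperature rows cannot describe subjects on drug.

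**Working it through.** The plan states no figure for this table, so there is nothing to reproduce. The check has two parts.

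**1. The criteria against the rule they should implement**

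| Sign | Criteria | Absolute, no baseline condition |
|---|---|---|
| Blood pressure | 2 | 2 |
| Respiration | 2 | 2 |
| Pulse | 4 | 2 |
| Temperature | 2 | 1 |
| Weight | 2 | 0 |
| Total | 12 | 7 |

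SAP 8.7.3 shows that the omission is not a general convention. For laboratory tests, a treatment-emergent high needs a baseline at or below the upper limit and a later value above it, and the mirror rule applies to lows. The 1.1°C temperature row in 8.7.4 likewise states a baseline condition. The absolute rows state none.

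Baseline exceeders can enter the trial. Inclusion criterion 11 requires hypertensive patients to be controlled on stable medication for at least 8 weeks before Screening, but neither it nor any other entry criterion sets a ceiling in mmHg.

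**2. Size of the dilution**

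All inputs here are assumptions, because the documents give neither baseline shares nor event rates:

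- b = share of each arm beyond the limit at baseline, equal across arms: 5%, 10% or 20%
- every one of these subjects exceeds the limit again after baseline
- p = rate of newly exceeding among the rest: 10% on placebo, 20% on active drug

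Reported rate = b + (1 − b) × p. The difference between arms is therefore (1 − b) × (0.20 − 0.10). With a baseline condition and an at-risk denominator, the result is 10% against 20% for any b: difference 10 points, ratio 2.0.

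| b | Placebo | Active | Difference | Ratio |
|---|---|---|---|---|
| 0% | 10.0% | 20.0% | 10.0 points | 2.00 |
| 5% | 0.05 + 0.95 × 0.10 = 14.5% | 0.05 + 0.95 × 0.20 = 24.0% | 9.5 points | 1.66 |
| 10% | 0.10 + 0.90 × 0.10 = 19.0% | 0.10 + 0.90 × 0.20 = 28.0% | 9.0 points | 1.47 |
| 20% | 0.20 + 0.80 × 0.10 = 28.0% | 0.20 + 0.80 × 0.20 = 36.0% | 8.0 points | 1.29 |

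Share of counted subjects who were already beyond the limit at baseline:

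- b = 5%: 5/14.5 = 34% on placebo, 5/24 = 21% on active drug
- b = 10%: 10/19 = 53% and 10/28 = 36%
- b = 20%: 20/28 = 71% and 20/36 = 56%

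If only 80% of baseline exceeders exceed again, b = 10% gives 0.08 + 0.09 = 17% against 0.08 + 0.18 = 26%, a ratio of 1.53 instead of 1.47.

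**The case against.** The strongest reply is that the sentence above the list speaks of changes from baseline, that the SAP is to be read together with the protocol, and that the protocol calls these changes treatment-emergent. A careful programmer could infer that a subject already beyond the limit is not counted. That reading is possible, but no rule states it. The list beneath the sentence is what will be programmed, and 8.7.3 and the 1.1°C row show that the SAP writes a baseline condition where it intends one.

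The second reply is that the harm is small. The by-visit change summaries and the by-subject listing are not diluted, and SAP 8.7 plans no safety tests. The difference in percentage points also shrinks much less than the ratio. All of this stands and limits the point to one descriptive table. It does not remove the point, because mean changes cannot stand in for a count of subjects who newly cross a limit.

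Two stronger readings are tempting. A reader might infer that the whole vital-sign table ignores baseline; five of the 12 criteria show otherwise. A reader might also infer that the blood-pressure counts will consist mostly of pre-existing hypertension. The documents give no baseline distribution, the controlled-pressure criterion argues against a large share, and in the illustration existing cases are a majority in both arms only at b = 20%.

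A further fair objection concerns the remedy. The blood-pressure rows join systolic and diastolic limits with an or. Excluding anyone who meets the joint row at baseline would drop a subject whose diastolic pressure is 101 on Day 1 and whose systolic pressure later climbs from 140 to 190. The fix has to avoid that.

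**Conclusion.** The point holds for the seven absolute criteria. SAP 8.7.4 does not supply the treatment-emergent definition that Protocol 11.7.5 delegates to it, and its absolute limits, applied as written, count existing exceedances as changes. For any b above zero, with equal baseline shares, the difference shrinks by (1 − b) and the ratio moves toward 1. The direction follows from the arithmetic; the size does not come from the documents. The ratios of 1.66, 1.47 and 1.29 rest on assumed baseline shares, assumed event rates and the assumption that every baseline exceeder exceeds again.

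The practical weight falls on the row with systolic above 150 or diastolic above 100. For respiration and the more extreme limits, few subjects are likely to start beyond the limit, which is also an assumption. No test or decision rule is affected, so this should be corrected but is not critical to the trial's conclusions. The temperature timing is a separate matter of fact: no scheduled post-Day 1 temperature is taken on drug.

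**What to change.** In SAP 8.7.4:

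1. For each absolute criterion, count a subject only if the baseline value did not meet it and at least one post-baseline value did. Use as denominator the subjects who did not meet it at baseline. Apply this to systolic and diastolic pressure separately, so that a raised value in one does not remove the subject from the other.
2. Add a table of baseline category against worst post-baseline category for systolic and for diastolic pressure, so that worsening in subjects with a raised baseline stays visible. If the bands use only the SAP's own limits, a rise from 155 to 195 mmHg stays in one cell. The sponsor should choose bands with that in mind, or point readers to the by-visit changes and the listing.
3. Show off-drug end-of-study readings in their own row. For temperature this is the only scheduled post-baseline row and should be labelled as such.

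The limits themselves need no change for this purpose. The cost is a few sentences, slightly more programming and one extra table. No new data are needed. If the SAP is not reopened, its Section 1 already provides for describing and justifying such a deviation in the clinical study report.

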#### **Criteria for clinically significant changes in vital signs parameters.**

##### Pulse Rate

- < 50 bpm
- >120 bpm
- 30 bpm increase from baseline

- 30 bpm decrease from baseline

#### Blood Pressure

- SBP > 150 mmHg or DBP > 100 mmHg
- SBP > 200 mmHg or DBP > 110 mmHg

#### Respiration Rate

- < 8 breaths/min
- 40 breaths/min

#### Temperature

- 38.3°C
- 1.1°C increase from baseline (Baseline > 36.8°C)

#### Change in Weight

- 5% increase from baseline
- 5% decrease from baseline

A by-subject listing will be provided.

### **8.7.5 Physical examinations**

A full physical examination will be conducted at screening, week 12 and EOS as indicated in the schedule of assessments and will include a review of the following systems: head/neck/thyroid; eyes/ears/nose/throat (EENT); respiratory; cardiovascular; chest; lymph nodes; abdomen; skin; musculoskeletal; Neurological; Breast; anorectal, and genital examinations will be performed when medically indicated.

Physical examination data will be provided in data listings.

### **8.7.6 Electrocardiograms (ECG)**

12-lead ECG measurements include (Heart Rate (bpm), QRS Duration (msec), PR Interval (msec), QT Interval (msec), RR Interval (msec) and QTcF (msec)) and will be summarized using an 8-number summary by visit and treatment for all safety subjects for observed values and changes from baseline. The overall ECG interpretation (Normal, Abnormal Not Clinically Significant, Abnormal Clinically Significant) will be summarized by presenting the number and percentage of subjects for each treatment group and time-point.

In addition, the number and percentage of subjects meeting or exceeding the following categories will be summarized by treatment group.

- Absolute QT/QTc interval prolongation
  - QTc interval > 450
  - QTc interval > 480
  - QTc interval > 500

- Change from baseline in QTc interval
  - QTc interval increases from baseline >30
  - QTc interval increase from baseline >60

A by-subject listing will be provided.

## **8.8 Pharmacokinetics (PK) and Pharmacokinetics/Pharmacodynamics (PK/PD) Analysis**

During the study, PK samples and PD samples for FGF19, C4 and bile acid will be collected as shown in the [schedule of assessments](#). On day 1 and weeks 12, 36, and 72, a sample will be collected predose and two samples postdose; the first postdose sample will be collected 1 to 3 hours postdose and the second postdose sample at least 1 hour later. At all other visits, PK samples will be collected predose.

### **8.8.1 Pharmacokinetic Analyses**

The PK analysis will use the pharmacokinetic population and will include only subjects in active treatment arms.

The concentration data for EDP-305 and each metabolite collected according to schedule of events and will be summarized by active treatment arm, visit, and nominal time point. Concentrations that are below the limit of quantitation (BLQ) will be treated as zero for the computation of descriptive statistics. If more than 50% of subjects have postdose concentration values below BLQ, descriptive statistics will not be presented except for maximum and BLQ will be displayed for mean and minimum. The number of observations, arithmetic mean, standard deviation (SD), % coefficient of variation (%CV), median, minimum, maximum, geometric mean, and %CV of the geometric mean (%GCV) will be displayed.

Individual data will be presented in listing.

### **8.8.2 Pharmacodynamic Analyses**

The PD analysis will be based on subjects' randomized treatment assignment using all subjects belonging to the ITT population with available dosing data. This will include all treatment arms (active and placebo).

A descriptive summary will be provided for the FGF19, C4, and bile acid endpoints including measured concentrations, change from baseline, and percentage change from baseline using the 8-number summary by visit, treatment group, and bin time midpoint.

A by-subject listing will be provided for observed and derived variables.

### **8.8.3 Pharmacokinetics/Pharmacodynamics (PK/PD) Analysis**

Scatter plots will be created using all subjects in the PK population. Plots for percentage change from baseline in each PD activity with EDP-305 concentration value will be generated for week 12 pre-dose.

Additionally the following PK/PD plots will be created using all subjects in the PK population. Other PD plots will be created using all subjects in the efficacy population,

## Final Analysis

### Statistical Analysis Plan (SAP)

including placebo, as applicable. The following scatterplots will be generated:

- Percentage change from Baseline in ALT with the percentage change from Baseline in FGF19 (Predose Week 12)
- Percentage change from Baseline in ALT with the percentage change from Baseline in C4 (Predose Week 12)
- Percentage change from Baseline in ALT with the percentage change from Baseline in Bile Acid (Predose Week 12)
- Percentage change from Baseline in ALT with EDP-305 concentration value (predose at Week 12)
- Percentage change from Baseline in GGT with the percentage change from Baseline in FGF19 (Predose Week 12)
- Percentage change from Baseline in GGT with the percentage change from Baseline in C4 (Predose Week 12)
- Percentage change from Baseline in GGT with the percentage change from Baseline in Bile Acid (Predose Week 12)
- Percentage change from Baseline in GGT with EDP-305 concentration value (Predose Week 12)
- Percentage change from Baseline in Alkaline Phosphatase with the percentage change from Baseline in FGF19 (Predose Week 12)
- Percentage change from Baseline in Alkaline Phosphatase with the percentage change from Baseline in C4 (Predose Week 12)
- Percentage change from Baseline in Alkaline Phosphatase with the percentage change from Baseline in Bile Acid (Predose Week 12)
- Percentage change from Baseline in Alkaline Phosphatase with EDP-305 concentration value (Predose Week 12)
- Percentage change from Baseline in MRI-PDFF with the percentage change from Baseline in FGF19 (Predose Week 12)
- Percentage change from Baseline in MRI-PDFF with the percentage change from Baseline in C4 (Predose Week 12)
- Percentage change from Baseline in MRI-PDFF with the percentage change from Baseline in Bile Acid (Predose Week 12)
- Percentage change from Baseline in MRI-PDFF with EDP-305 concentration value (Predose Week 12)

## Final Analysis Statistical Analysis Plan (SAP)

- Percentage change from Baseline in MRE with the percentage change from Baseline in FGF19 (Predose Week 12)
- Percentage change from Baseline in MRE with the percentage change from Baseline in C4 (Predose Week 12)
- Percentage change from Baseline in MRE with the percentage change from Baseline in Bile Acid (Predose Week 12)
- Percentage change from Baseline in MRE with EDP-305 concentration value (Predose Week 12)
- Percentage change from Baseline in ALT with the percentage change from Baseline in FGF19 (Predose Week 72)
- Percentage change from Baseline in ALT with the percentage change from Baseline in C4 (Predose Week 72)
- Percentage change from Baseline in ALT with the percentage change from Baseline in Bile Acid (Predose Week 72)
- Percentage change from Baseline in ALT with EDP-305 concentration value (predose at Week 72)
- Percentage change from Baseline in GGT with the percentage change from Baseline in FGF19 (Predose Week 72)
- Percentage change from Baseline in GGT with the percentage change from Baseline in C4 (Predose Week 72)
- Percentage change from Baseline in GGT with the percentage change from Baseline in Bile Acid (Predose Week 72)
- Percentage change from Baseline in GGT with EDP-305 concentration value (Predose Week 72)
- Percentage change from Baseline in Alkaline Phosphatase with the percentage change from Baseline in FGF19 (Predose Week 72)
- Percentage change from Baseline in Alkaline Phosphatase with the percentage change from Baseline in C4 (Predose Week 72)
- Percentage change from Baseline in Alkaline Phosphatase with the percentage change from Baseline in Bile Acid (Predose Week 72)
- Percentage change from Baseline in Alkaline Phosphatase with EDP-305 concentration value (Predose Week 72)

## Final Analysis

### Statistical Analysis Plan (SAP)

- Percentage change from Baseline in MRI-PDFF with the percentage change from Baseline in FGF19 (Predose Week 72)
- Percentage change from Baseline in MRI-PDFF with the percentage change from Baseline in C4 (Predose Week 72)
- Percentage change from Baseline in MRI-PDFF with the percentage change from Baseline in Bile Acid (Predose Week 72)
- Percentage change from Baseline in MRI-PDFF with EDP-305 concentration value (Predose Week 72)
- Percentage change from Baseline in MRE with the percentage change from Baseline in FGF19 (Predose Week 72)
- Percentage change from Baseline in MRE with the percentage change from Baseline in C4 (Predose Week 72)
- Percentage change from Baseline in MRE with the percentage change from Baseline in Bile Acid (Predose Week 72)
- Percentage change from Baseline in MRE with EDP-305 concentration value (Predose Week 72)

Box plot of EDP-305 and EP-022679 concentration (last predose) for subjects with adverse events occurring in at least 5% of the combined active subjects.

Lastly, the analyses below will be carried out to provide additional data for better understanding of specific clinical events and manifestations during the course of the study. These analyses will be conducted for subjects with or without pruritus:

#### **PK and pruritus:**

- Summary of plasma concentration of EDP-305 and EP-022679 per time point and treatment group by visit for subjects with and without pruritus
- Summary of PK parameters by treatment group by visit for subjects with and without pruritus
- Boxplot of predose concentration at Week 2,4,8 and 12 for EDP-305 and EP-022679 by treatment group for subjects with and without pruritus
- Listing of EDP-305 and EP-022679 concentration value for subjects with pruritus

#### **C4 and pruritus:**

- Summary of C4, change from baseline and percentage change from baseline by hour by visit for subjects with and without pruritus
- Summary of AUC0-8 and AUC2-8 for C4, change from baseline and percentage change from baseline at Week 12 for subjects with and without pruritus

## 8.9 Subgroup Analysis

Subgroup analyses will be performed for the primary endpoint and the secondary endpoints to determine whether significant differences exist in primary and secondary endpoint results between subgroups.

These subgroup analyses will be carried out using the subjects from the ITT and PP population.

The list of potential subgroups (with applicable definitions in parentheses) includes the following:

- Baseline Fibrosis score (2, 3),
- MRE week 72 response: (<15% reduction vs  $\geq$ 15% reduction in percentage of change from baseline),
- MRI-PDFF week 72 response: (<30% reduction vs  $\geq$ 30% reduction in percentage of change from baseline),
- Both MRE week 72 response ( $\geq$ 15% reduction in percentage of change from baseline) and MRI-PDFF week 72 response ( $\geq$ 30% reduction in percentage of change from baseline) vs non-response.

A logistic regression model will be used for categorical endpoints. The model will include the treatment group, diabetes status, use of Vitamin E and/or pioglitazone, subgroup and subgroup-by-treatment interaction as fixed effects and baseline NAS score as covariate. Odds ratios and 95% confidence intervals will be reported.

For continuous endpoints an ANCOVA model with treatment group, diabetes status, use of Vitamin E and/or pioglitazone, subgroup and subgroup-by-treatment interaction as fixed effects and baseline NAS along with baseline parameter of interest as covariates. Least-squares means (using type III sum-of-squares), standard errors, p-value and 2-sided 95% confidence interval for treatment differences will be reported.

For continuous endpoints that are repeated over visits a MMRM technique will be used. The model will include treatment, visit, subgroup and interaction effect of treatment, visit and subgroup as fixed effects and baseline NAS along with baseline parameter of interest as covariates. Least-squares means (using type III sum-of-squares), standard errors, p-value and 2-sided 95% confidence interval for treatment differences will be presented for each visit

Forest plots will be presented for the sub group analysis mentioned above to describe the association using ITT and PP population.

